10.8 Receipt, Storage, Dispensing, and Return

Upon receipt, trial personnel will verify the contents of all supplies received and promptly notify the appropriate contacts of any discrepancies or damages. Only authorized trial personnel may administer trial treatment, and only subjects randomized in the trial may receive trial treatment. The investigator is responsible for ensuring an accurate record of inventory is maintained. The investigator or designee will keep a current record of the trial-device delivery to the trial site, inventory, and treatment dispensation, and this record will be made available to the sponsor upon request. Sites will be queried about any discrepancies.

All trial devices must be stored in a secure area.

After the last subject has received treatment, and after verification of device accountability, it is the investigator's responsibility to return all used and unused IMD equipment (i.e., console, handpiece, and transducers) to the local depot. Appropriate records of return must be maintained for accountability purposes.

All device-accountability procedures must be completed before the trial is considered complete.

10.9 Device Accountability Procedures

All necessary trial supplies will be released to the investigator before site initiation at the latest. Accountability for trial supplies at the trial site is the responsibility of the investigator.

Access to the IMD will be controlled, and the IMD will be used only in the clinical trial and according to the CTP. The sponsor will keep records to document the physical location of all IMDs from shipment to the investigative sites until return. The investigator or an authorized designee is responsible for ensuring accurate records of receipt, use, and return of the IMD, are maintained and include:

- The date of receipt and quantity of units received.
- Identification of each IMD (batch number/serial number or unique code).
- The expiry date (if applicable).

- The names of all persons who received or used each device.
- The date or dates of use and time.
- Subject identification.
- Date of return of used, unused, expired, or malfunctioning IMDs (if applicable).

Dispensing records (i.e., treatment lines administered, and energy levels used) are recorded on the subject's treatment record, which is automatically generated by the Ulthera DeepSEE System. These data will be transferred to the EDC system. An overall accountability log will be maintained for each subject, documenting the number of treatment lines administered as well as energy levels used in each treatment region.

All used and unused IMD equipment must be returned to the local depot immediately after the trial is completed (Section 10.8). Products destroyed during shipment or at an investigative site should be accounted for and documented. All clinical supplies must be accounted for at the termination of the trial and a written explanation provided for discrepancies.

10.10 Treatment Compliance

All treatments will be administered by the primary treating investigator or designated back-up treating investigators; therefore, assessment of compliance is unnecessary. Variations from the defined trial-treatment administration will be reported as protocol deviations.

10.11 Duration of Trial

Subjects will have a screening period up to 14 days and participate for a maximum duration of 180 days (\pm 14 days) after treatment.

The estimated trial duration from first subject, first visit (FSFV) to last subject, last visit (LSLV) will be approximately 15 months, including an estimated 9 months for subject recruitment to complete. The actual duration of the study will be calculated according to the actual date of the Clinical Study Report stamp.

11 TRIAL PROCEDURES

11.1 Visit Schedule

The investigation activities and visit schedule are detailed in the Schedule of Events

The screening visit (V1) is required to determine subject eligibility for trial participation; this visit must be completed -14 to -3 days prior to Day 1 (V2). Eligible subjects will be randomized during the screening period (Day -14 to -3) to either the Treatment Group or Control Group.

At Day 1, the Treatment Group will receive a single treatment with the Ulthera DeepSEE System to the midface, lower face, submentum, and upper neck with three DS transducers (DS 10-1.5, DS 7-3.0, DS 7-4.5). The Control Group will not receive treatment at Day 1, and will remain untreated until Day 90. Following completion of all protocol-mandated assessments at Day 90, the Control Group will receive a single treatment with the Ulthera DeepSEE System to the midface, lower face, submentum and upper neck with three DS transducers (DS 10-1.5, DS 7-3.0, DS 7-4.5).

All treatments should be administered at the investigative site by the primary treating investigator or designated back-up treating investigators, occurring only after completion of all required pre-treatment procedures and assessments.

Following treatment with the Ulthera DeepSEE System, subjects will be observed for a minimum of 30 minutes. Subjects in both trial groups will be contacted by telephone at 3 days (\pm 1 day) and 14 days (\pm 3 days) after treatment and will have an unscheduled visit if necessary due to safety concerns (Section 11.1.2).

Safety follow-up will occur until Day 180 ± 14 days (V4) for both trial groups, corresponding to 180 days post-treatment for the Treatment Group and 90 days post-treatment for the Control Group.

The primary endpoint visit will occur at Day 90 (\pm 7 days) post-treatment, and the EOT visit will occur at Day 180 (\pm 14 days). In the case of a subject's premature discontinuation of the trial, a final assessment (EOT visit) should be performed.

11.1.1 Scheduled Visits

All scheduled visits and applicable trial assessments must occur as noted in Section 11.1 and the Schedule of Events.

11.1.2 Unscheduled Visits

To ensure subject safety, any subject who, for any reason, requires additional follow-up that does not coincide with a scheduled trial visit should have that visit recorded as an unscheduled visit, during which concomitant medication/procedures and AEs must be assessed and recorded.

[figure not shown]
An unscheduled visit must be scheduled if information acquired from a subject during a post-treatment phone call, requires additional follow-up as determined by the investigator.

[figure not shown]
11.2 Trial Assessments and Definitions

11.2.1 Effectiveness Assessments

The effectiveness the Ulthera DeepSEE System for the treatment of skin laxity in the lower face and submental area will be evaluated using several assessments. Refer to the respective endpoints (Section 7.2), visit schedule (Section 11.1), and Schedule of Events for additional information on the methods and timing of effectiveness assessments.

11.2.1.4 FACE-Q Assessment

FACE-Q is a set of validated, standardized patient-reported outcome scales for subjects receiving facial cosmetic procedures. [14-16] In this trial, subjects will evaluate treatment outcomes using the FACE-Q Satisfaction with Lower Face and Jawline instrument. Subjects will utilize a mirror when answering the FACE-Q questionnaire. Standardized mirrors will be provided to sites to ensure subjects are utilizing the same type of mirror (i.e., standard size, shape, etc.).

For each subject, a sum score (range: 5 to 20) will be calculated; higher scores indicate a better outcome. Sum scores will then be Rasch-transformed (range: 0 to 100)

11.2.1.5 Subject Global Aesthetic Improvement Scale (sGAIS)

Subjects will self-report using the sGAIS (Appendix 16.5.1) to assess overall aesthetic improvement of the lower face, submentum, and neck

If a subject responds "no change", "worse", "much worse", or "very much worse" via sGAIS assessment, they will be asked to explain their choice of rating.

For completion of the sGAIS, subjects will use the same standardized mirror provided for FACE-Q assessment.

11.2.1.6 Treating Investigator Global Aesthetic Improvement Scale (iGAIS)

Treating investigators will use the iGAIS to assess overall aesthetic improvement of the lower face, submentum, and neck

11.2.2 Safety Assessments

Standard safety assessments, including documentation of AEs and SAEs reported by the investigator throughout the trial, will be evaluated.

Refer to the respective endpoints (Section 7.2.2) and the Schedule of Events for additional information on the safety assessments.

11.2.2.1 Adverse Events (AEs) / Serious Adverse Events (SAEs)

[figure not shown]
All AEs/SAEs reported by trial subjects, investigators, or other trial personnel after the time of informed consent through the EOT Visit (V4) will be recorded. All AEs/SAEs will be recorded regardless of causality. Additional information (e.g., definitions, reporting requirements) is provided in Section 12. All AEs/SAEs will be assessed throughout the trial, including on-site trial visits and during follow-up phone calls.

Any AE/SAE must be documented in the subject's file and on the AE eCRF page.

Any AE/SAE observed will be fully investigated, documented, and followed until the AE/SAE is either resolved or adequately explained, or until the EOT Visit (Section 12.2.2).

Serious AEs occurring after the end of the observational period only need to be reported if the investigator considers the SAE to be related to the investigational device. These reports generally will not be entered into the clinical database.

[figure not shown]

11.2.3 Additional Data Collected

Data for other assessments will be collected as follows:

- Demographics and other baseline characteristics, including height and weight;
- Dispensing records (i.e., treatment lines administered, and energy levels used);
- Relevant medical history/concomitant diseases;
- Concomitant medications and non-drug treatments; and
- Vital signs.

11.2.3.2 Vital Signs

Vital signs will be measured on all subjects after they have been seated for approximately five minutes. Resting heart rate and blood pressure (systolic and diastolic, preferably on the same arm each time) will be measured at screening (V1) and at the End of Trial Visit (V4).

11.2.4 Appropriateness of Assessments

Appropriateness of the selected trial assessments is detailed in the respective Effectiveness Assessments (Section 11.2.1) and Safety Assessments (Section 11.2.2).

12 SAFETY DEFINITIONS AND REPORTING REQUIREMENTS

12.1 Definition of an Adverse Event (AE)

An AE is any untoward medical occurrence, unintended disease or injury, or untoward clinical sign (including an abnormal laboratory finding) in subjects, users, or other persons, whether or not related to the IMD.

Note:

- 1. This definition includes events related to the IMD.
- 2. This definition includes events related to the procedures involved.
- 3. For users or other persons, this definition is restricted to events related to the IMD.

12.1.1 Details of an AE

The period of observation for an AE extends from when the ICF is signed until the subject's last trial visit. Any medical occurrence between the time the ICF is signed and the first treatment with the IMD is an AE and has to be documented in the subject's file and on the AE eCRF page. Any observed AE will be fully investigated, documented, and followed until the event is either resolved or adequately explained, or until the EOT visit. In cases of surgical or diagnostic procedures, the condition/illness leading to such a procedure is considered the AE rather than the procedure itself. New AEs reported to the investigator during the observational period, after the last treatment with the IMD, must be documented, treated, and followed like all other AEs.

Treatment-emergent AEs (TEAEs) are defined as AEs with onset at or after the first administration of trial treatment. If an AE starts prior to treatment but worsens at or after treatment, the investigator records this observation as a new AE with onset at the time of worsening.

A pre-existing condition noted in the medical history should not be reported as an AE, unless the condition worsens or the disease reoccurs during the reporting period. To determine whether a condition has worsened, it is compared to the subject's condition at screening.

Elective treatments planned before screening, and which are documented in the subject's source data, are usually not regarded as AEs. However, elective procedures should be postponed, if possible, until the subject completes their participation in the trial.

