10.5.2 Selection and Timing of Treatment for Each Subject

Subjects in the Treatment Group will receive a single treatment with the Ulthera DeepSEE System at Day 1 (V2). Subjects in the Control Group will not receive treatment at Day 1 and will remain untreated until Day 90 (V3). Following completion of all protocol-mandated assessments at Day 90 (Section 11.1), the Control Group will receive a single treatment with the Ulthera DeepSEE System.

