6.4 Special Statistical/Analytical Issues

6.4.2 Baseline and Pre-treatment

Baseline is defined for both treatment group and control group as the last observed value or test result before Day 1. Pre-treatment is as same as baseline in treatment group and defined as the last observed value or test result before Day 90 treatment in control group.

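### Worsening of a medical-history condition is judged only against screening, about three months before Controls are treated, so one narrow kind of post-treatment flare in Controls goes unreported

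*Protocol*

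**What the plan says.** Four rules in Protocol 12.1.1 matter here.

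- Medical-history conditions: "A pre-existing condition noted in the medical history should not be reported as an AE, unless the condition worsens or the disease reoccurs". For the worsening test, "it is compared to the subject's condition at screening". No other reference is given for Controls.
- Events before treatment: "Any medical occurrence between the time the ICF is signed and the first treatment with the IMD is an AE". For Controls this covers the whole untreated wait.
- Events that straddle treatment: "If an AE starts prior to treatment but worsens at or after treatment, the investigator records this observation as a new AE". That new event is dated from when the worsening began.
- Treatment-emergent events are those with onset at or after the first trial treatment. SAP 5.2.3.1 applies this by group, so for Controls the start date must be on or after the Day 90 treatment.

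On timing, Protocol 11.1 puts screening 3 to 14 days before Day 1, when the Treatment Group is treated. Protocol 10.5.2 says: "Subjects in the Control Group will not receive treatment at Day 1 and will remain untreated until Day 90".

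On use, the secondary safety endpoint is the incidence of device-related treatment-emergent events. SAP 6.2 analyses it in all treated subjects, with the randomized groups pooled by default and tables by group and overall.

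SAP 6.4.2 has a separate pre-treatment reference for Controls, "defined as the last observed value or test result before Day 90 treatment in control group". It concerns values and test results, not adverse events.

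**The concern.** A worsening rule for treatment-emergent events should compare the subject after treatment with the subject just before it. Screening is a fair stand-in for that state in the Treatment Group. In Controls it describes the subject about three months earlier, and a fluctuating condition can change in that time.

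If the condition has improved by Day 90, the screening level is too lenient a threshold. A flare after treatment can rise clearly above the immediate pre-treatment state and still not exceed the screening level. Read literally, the rule then tells the investigator not to report it. The error runs in one direction: it removes events that follow device exposure.

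Protocol 8.2 gives delayed treatment to Controls partly to enlarge the safety database. The reporting rule should therefore fit those exposures as well as it fits the Day 1 exposures. Protocol 6.3 lists headache, migraine, rash, pruritus and discoloration among post-market reports, and conditions of this kind can fluctuate.

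**Working it through.** **Headcount.** Protocol 9.1 plans about 250 screened with 20% screen failure: 250 × (1 − 0.20) = 200 randomized, which matches the plan. At 1:1 that is 100 per group. The documents give no figure for the worsening rule itself.

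**Gap from screening to treatment.**

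- Treatment Group: 3 to 14 days (Protocol 11.1).
- Controls, Day 90 visit taken as 90 days after Day 1: 90 + 3 = 93 to 90 + 14 = 104 days. With the ±7-day window, 83 + 3 = 86 to 97 + 14 = 111 days.
- Controls, Day 90 visit taken as 89 days after Day 1: 82 + 3 = 85 to 96 + 14 = 110 days.

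Protocol 11.1 states the ±7-day window for the primary endpoint visit; applying it to the Controls' treatment visit is an assumption. On any count the gap is about three months.

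**Which courses the rules capture in a Control.** The severity words are illustrative.

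| Screening | Just before Day 90 treatment | After treatment | Result under the written rules |
|---|---|---|---|
| mild | mild | moderate | Worse than screening, onset after treatment: captured |
| moderate | resolved | moderate | Disease has recurred: captured |
| mild | moderate | moderate | Adverse event with onset during the wait; not treatment-emergent: correct |
| mild | moderate | severe | Event during the wait, then a new event at the further worsening: captured |
| moderate | mild | severe | Worse than screening: captured |
| absent; began after consent | mild | moderate | Already an adverse event, worsens after treatment: new event, captured |
| **moderate** | **mild, not resolved** | **moderate** | **Not worse than screening, not clearly a recurrence: not reported** |

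Only the last row fails. It shows the same change across treatment as the row above it, mild to moderate, but is handled differently because the condition was in the medical history. The straddling rule does not reach it, because an improved medical-history condition is not an adverse event to begin with. The rule on events before treatment does not reach it either, because the flare comes after treatment. SAP 5.2.3.1 classifies only what has already been recorded as an adverse event.

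**Size per missed subject.** Control rate: 1/100 = 1.0 percentage point. Pooled rate: 1/200 = 0.5 point. If 20% of Controls were lost before Day 90 (assumed), 80 would be treated: 1/80 = 1.25 points and 1/180 = 0.56 point.

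**How many.** Let p be the share of Controls with a relevant medical-history condition, q the share of those that ease without resolving by Day 90, and r the share of those that flare to no worse than screening. Missed Controls = 100 × p × q × r. The documents give none of these rates, so the values are assumptions.

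| p = q = r | Missed Controls | Share of 200 treated |
|---|---|---|
| 10% | 0.1 | 0.05% |
| 30% | 2.7 | 1.35% |
| 50% | 12.5 | 6.25% |

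These counts precede the judgement of device-relatedness, so the effect on the endpoint is smaller again.

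**The case against.** The strongest case against is that the surrounding rules leave little uncovered. Six of the seven courses above are handled correctly, adverse events are assessed at on-site visits and phone calls, and onset dates are recorded. Many candidate conditions are episodic, and an investigator could reasonably call a new headache or rash episode a recurrence. Subjects must be healthy, and scarring or open wounds in the treatment area are excluded. The event must also be judged device-related. The safety tables are descriptive, with no visible between-group test. All of this stands and keeps the effect small. It does not remove the case, because for a continuing condition that eased and flared, reporting depends on how each investigator reads recurrence.

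A reader might infer that the rule also works in reverse, so that a condition which worsened during the wait is counted against the device. The documents do not support that. Such a worsening exceeds the screening level, so it is an adverse event with onset before treatment and is not treatment-emergent under SAP 5.2.3.1. Mis-assignment would need an unreported event or a wrong onset date, which is an error of execution.

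A reader might also see a contradiction with SAP 6.4.2. There is none, since that section governs values and test results. It shows only that the SAP already uses a separate pre-treatment reference point for Controls.

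**Conclusion.** The point holds as a minor gap in the reporting rule. It under-counts treatment-emergent events in Controls in one specific course and leaves the two halves of the pooled safety set with different effective reference points. Of the three related-event summaries in SAP 6.2.1, the overall one and the one to 90 days after treatment include Controls. The Day 180 summary covers the Treatment Group only and is untouched, as is the primary effectiveness analysis.

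It would be wrong to conclude that flares in about half of the treated subjects may be missed. Controls are 100/200 = 50% of treated subjects if none is lost, but that is the share under the rule with the long gap. The share affected is unknown and probably small.

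The conclusion rests on a literal reading of Protocol 12.1.1 and on its visible text. Parts of the adverse-event collection text in Protocol 12.1.2 and the Schedule of Events cannot be seen.

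**What to change.** In Protocol 12.1.1 and the eCRF completion guide, state that for events at or after treatment, worsening is compared with the subject's condition immediately before that subject's treatment: Day 1 for the Treatment Group, and the Day 90 visit before delayed treatment for Controls. Keep screening as the reference for events before treatment.

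The cost is one sentence in each document and one item of recording. Because an improved medical-history condition is not an adverse event, routine adverse-event questioning at Day 90 would not necessarily capture its status. Sites would need to note the status of ongoing medical-history conditions at that visit before treating. No extra visit is needed, and sample size, power and type I error are unaffected.

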12.1.2 Reporting and Handling of an AE

Data pertaining to AEs will be collecte

. The investigator will assess and

record any AE in detail in the subject's file and on the AE eCRF. The following information must be recorded:

- AE diagnosis or main symptom;
- AE localization (restricted to treatment area, systemic). If a local reaction, the corresponding area should be reported;
- Date of onset;
- Intensity (maximum observed using the Severity Grading scale; Section 12.1.3);
- Causal relationship (not related, related) to investigational device and study procedure;
- Serious (yes, no), date serious since, and reason for seriousness;
- Outcome (Section 12.1.5);
- AE leading to discontinuation of the clinical trial (yes, no);
- Action taken with medical device;
- Action taken related to the AE; and
- Stop date.

In cases of an SAE (defined in Section 12.2), the investigator must also complete an SAE Report Form and report it to the sponsor and CRO immediately as described in Section 12.2.2.

12.1.3 Severity Grading for an AE

The clinical severity (i.e., intensity) of an AE will be classified as:

Mild: Signs and symptoms that can be easily tolerated. Symptoms can be ignored

and disappear when the subject is distracted.

Moderate: Signs and symptoms that cause discomfort and interfere with normal

functioning but are tolerable. They cannot be ignored and do not disappear

when the subject is distracted.

Severe: Signs and symptoms that affect usual daily activity and incapacitate the

subject, thereby interrupting daily activities.

The investigator is required to grade the severity (i.e., intensity) of each AE.

